4.4. Study population

The source population is all Danish citizens (popuation~5.8 million).²² The study population for risk analysis (the test-negative case-control analysis) will be all patients tested for SARS-CoV-2, while the prognosis analysis (cohort analysis) will only include patients tested positive SARS-CoV-2, *i.e.*, patients with COVID-19.

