4.7. Outcomes

The primary outcome is death within 30 days after positive test for SARS-CoV-2, obtained from the Danish Register of Causes of Deaths.²⁷

Secondary outcomes include hospital admission (in- or acute outpatient stay lasting > 12 hours) at day of or within 30 days after a positive test in patients not already admitted before the date of the test. In addition, outcomes include ICU admission, mechanical ventilation, and renal replacement therapy at day of or within 30 days after positive test for SARS-CoV-2. Secondary outcomes will be obtained from the Danish National Registry, 3rd version (LPR3).²⁴ While the coding has not yet been validated in this LPR3, admission to ICU, mechanical ventilation, and renal replacement therapy are all registered accurately (positive predictive values 96%-100%) in LPR2 as this is also the platform for mandatory reporting to the national database for quality of intensive care.^{28,29}

Finally, in the risk analysis, we identified patients with positive tests among all patients tested for SARS-CoV-2.

[figure not shown]

Figure illustrating the endpoints in the COVID-19 risk analysis and the endpoints in the COVID-19 prognosis analysis.

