4.8.2. Selection bias

The risk of selection bias is reduced by including all tested Danish inhabitants. Still, criteria for testing and hospital admission have changed during the study period, which will be addressed in a sensitivity analysis stratified by calendar time. We do not expect that ACE-I/ARB users would be more likely to be tested, and thereby included, as compared to users of other antihypertensive drugs.

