The risk of COVID-19 (a positive test for SARS-CoV-2) will be analyzed using a testnegative case-control design among all patients tested. All covariates will be tabulated for patients with a positive test and negative test for SARS-CoV-2. The odds ratio for current ACE-I/ARB use vs. non-use and CCB use, respectively, will be estimated using two separate logistic regression models adjusted for all covariates, see Appendix.

In a sensitivity analysis, we will explore the robustness of our findings by repeating the analyses in patients who filled a prescription within 120 days before a positive test.

Finally, we will do a sensitivity analysis stratified by calendar time to address changes in testing and hospitalization strategy.

10

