Acute renal replacement therapy (RRT) (in patients without chronic RRT)	DNPR/Procedure		BJFD0	BJFD2 (any codes within prior 12 months)
Treatment with inotropes/vasopressors	DNPR/Procedure		BFHC92A, BFHC92B, BFHC92C, BFHC92D, BFHC92E, BFHC93A, BFHC93B, BFHC93C, BFHC95	
Covariates				
Age	CPR			
Sex	CPR			
Calendar time (before / after lockdown)	DNPR			
Hospital-diagnosed hypertension	DNPR/ICD-10	10y	110, 115	
Stable angina pectoris (without procedures)	DNPR/ICD-10	10y	120, 1251, 1259	121, 122, 123, 1200
Stable angina pectoris or CABG/PCI procedures	DNPR/ICD-10	10y	120, 1251, 1259	121, 122, 123, 1200
	DNPR/Procedure	10y	KFNA, KFNB, KFNC, KFND, KFNE, KFNF, KFNG, KFNH20	I21, I22, I23, I200 (any diagnosis during hospital contact with
				contact the proc

				or within 10
				years before
Myocardial infarction	DNPR/ICD-10	10y	121, 122, 123	
Heart failure	DNPR/ICD-10	10y	150	
Stroke	DNPR/ICD-10	10y	160, 161, 163, 164	
Atrial fibrillation/flutter	DNPR/ICD-10	10y	148	
Heart valve disease	DNPR/ICD-10	10y	105, 106, 107, 108, 109.8, 134-137, 139, 151.1A, Q22, Q23	
Venous thromboembolism	DNPR/ICD-10	10y	126, 1801, 1802, 1803	
Diabetes	DNPR/ICD-10	10y	E10, E11, E12, E13, E14, O24, G63.2, H360, N083	O24.4
	NPD/ATC	10y	A10A, A10B	
Chronic pulmonary disease	DNPR/ICD-10	10y	J40, J41-J44, J45–J47, J60–J67, J68.4, J70.1, J70.3, J84.1, J92.0, J96.1, J98.2, J98.3	
Markers of smoking (diagnoses or medications for tobacco smoking or	DNPR/ICD-10	10y	J41-J44, F17, Z716, Z720	
chronic obstructive pulmonary disease)				
	NPD/ATC	10y	R03, N07BA	
Obesity diagnoses or medications	DNPR/ICD-10	10y	E66	
	NPD/ATC	10y	A08	
Alcoholism-related diagnoses or medication for alcohol deterrent	DNPR/ICD-10	10y	DF10, DE244, DG312, DG621, DG721, DI426, DK292, DK70, DK852, DK860, DQ860, DZ502, DZ714, DZ721	F100
	NPD/ATC	10y	V03AA, N07BB	
Kidney disease diagnosis	DNPR/ICD-10	10y	112, 113, N00–N05, N07, N11, N14, N18–N19, Q61, N08, E102, E112, E142	
End-stage renal disease (kidney transplant or dialysis)	DNPR/Procedure	10y	BJFD2	
	DNPR/Surgery	10y	KKAS	
	DNPR/ICD-10	10y	T861, Z940	
Liver disease	DNPR/ICD-10	10y	B18, B150, B160, B162, B190, I85, K70, K71, K72, K73, K74, K760, K76.6	
Dementia	DNPR/ICD-10	10y	DF00, DF01, DF02, DF03, DG30, DG310B, DG311, DG318, DG319	
	NPD/ATC	10y	N06D	
Cancer (including metastatic cancer)	DNPR/ICD-10	10y	C00-C96, D459, D46, D471, D473, D474, D475, CxxxM	C44
Concurrent antihypertensive medication (see exposures)	NPD/ATC			

Statins	NPD/ATC	90d	C10AA, C10B

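### The test-negative odds ratio pools all routes to testing without accounting for test setting; results should also be shown by admission status at the test

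*Protocol*

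**What the plan says.** Section 4.4 sets the population for the risk analysis: it "will be all patients tested for SARS-CoV-2". Section 4.9 repeats this, saying that the risk of a positive test "will be analyzed using a testnegative case-control design among all patients tested", and specifies "two separate logistic regression models adjusted for all covariates, see Appendix", one against non-use and one against CCB use.

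The Appendix lists age, sex, diagnoses, medications, marital status, rural or urban residence, and a single item related to testing policy: "Calendar time (before / after lockdown"). It lists no test setting, admission status at the test, symptoms or reason for testing.

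On selection, section 4.8.2 states: "The risk of selection bias is reduced by including all tested Danish inhabitants". It then concedes that "criteria for testing and hospital admission have changed during the study period". The response, in 4.9, is that "we will do a sensitivity analysis stratified by calendar time to address changes in testing and hospitalization strategy". Section 4.8.2 also expects no difference in the likelihood of testing, but says so only against users of other antihypertensives.

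Section 4.7 shows that some people were inpatients when tested: the hospital-admission outcome is counted "in patients not already admitted before the date of the test". That rule is not carried over to the test-negative analysis.

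**The concern.** A test-negative design protects against selection into testing to the extent that cases and controls reach the test by comparable routes. Someone swabbed during an existing admission and someone tested from the community may differ both in cardiovascular drug use and in the chance of a positive result. When both differ, setting confounds the pooled odds ratio.

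Calendar time cannot stand in for setting, because inpatients and community patients are tested within the same period. The remark in 4.8.2 on likelihood of testing gives no cover to the non-use comparison, which is one of the two odds ratios planned.

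The third aim rests on these two odds ratios. The sample is large enough that a modest residual bias could produce an interval excluding 1, and section 6 says evidence of adverse effects will be passed to the medicines agency.

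**Working it through.** The protocol states no odds ratio, power or precision for this analysis, so there is no figure of that kind to reproduce. The check asks how far pooling alone could move the odds ratio if the drug did nothing.

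**Inputs from section 4.10.** N = 96,224 tested and P = 7,515 positive, so positivity is 7,515/96,224 = 7.8% and there are 96,224 − 7,515 = 88,709 negatives. Expected ACE-I/ARB use is 17%, taken from a historical influenza or pneumonia cohort.

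**Assumed inputs (not in the protocol).** Share already in hospital (h), positivity in hospital (p_h), and ACE-I/ARB use in hospital (e_h) and elsewhere (e_c). Within each setting the true odds ratio is 1.

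**Formulas.**
- Positivity elsewhere: p_c = (0.0781 − h·p_h)/(1 − h)
- Exposed positives: a = N[h·e_h·p_h + (1 − h)·e_c·p_c]
- Unexposed positives: b = P − a
- Exposed negatives: c = N[h·e_h + (1 − h)·e_c] − a
- Unexposed negatives: d = N − P − c
- Pooled OR = ad/(bc), with a Woolf 95% interval

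**One case in full.** Take h = 0.20, p_h = 0.03, e_h = 0.25, e_c = 0.14. Then p_c = (0.0781 − 0.006)/0.80 = 0.090. The cells are a ≈ 1,116, b ≈ 6,399, c ≈ 14,473 and d ≈ 74,236. OR = (1,116 × 74,236)/(6,399 × 14,473) = 0.89.

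**Four crude scenarios.** The last two columns keep positivity and overall use fixed and shrink the exposure gap between settings to one half or one quarter. This is an assumed stand-in for what covariate adjustment might leave.

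| h | p_h vs p_c | e_h vs e_c | Crude OR (95% CI) | Half gap | Quarter gap |
|---|---|---|---|---|---|
| 20% | 4% vs 8.8% | 20% vs 16% | 0.97 (0.91–1.03) | 0.98 | 0.99 |
| 20% | 3% vs 9.0% | 25% vs 14% | 0.89 (0.84–0.96) | 0.95 | 0.97 |
| 30% | 3% vs 9.9% | 30% vs 12% | 0.76 (0.71–0.82) | 0.88 | 0.94 |
| 20% | 12% vs 6.8% | 25% vs 14% | 1.10 (1.03–1.17) | 1.05 | 1.02 |

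Overall ACE-I/ARB use in these rows is 16% to 17%, consistent with section 4.10.

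**Reading the table.**
- With no exposure gap, the pooled OR is 1.00 whatever the positivity difference. With 35% tested in hospital, equal exposure in both settings and positivity twice as high in hospital, it is 1.00. Both differences are needed.
- A null OR at this sample size, with 17% exposed, has a 95% interval of about 0.94 to 1.06, so a bias of 7% to 10% can be enough to exclude 1.
- Conditioning on setting returns 1.00 by construction.
- A wider assumed grid (20% to 50% tested in hospital, use there 22% to 30%, positivity ratio 0.5 to 2) gives crude pooled ORs from 0.69 to 1.36. The result depends heavily on inputs the protocol does not supply.

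**The case against.** The strongest reply is that these are crude odds ratios, whereas the plan adjusts for age, sex, comorbidity, concurrent antihypertensives and many other drugs. Being older and taking more cardiovascular drugs is what those covariates capture. Setting biases the adjusted estimate only if ACE-I/ARB use still differs by setting given all of them. This stands: the size of the residual is unknown and the crude values should not be read as the expected bias. It does not remove the problem, since adjusting for patient characteristics is not conditioning on the route to the test.

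Second, the CCB comparison protects against much of this, because the share using ACE-I/ARB rather than CCB may be similar across settings. That also stands, though the protection is incomplete if the share still differs. A reader might infer that both odds ratios are equally at risk; the documents do not support that.

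Third, a reader might infer that the odds ratio in patients not yet admitted should become the main result. The protocol gives reason for caution. Section 4.9 anticipates outcomes occurring in the days before a positive test, so prior admission may itself result from COVID-19, and the secondary aim asks whether ACE-I/ARB use affects admission. Restricting on admission could therefore add selection bias. It would also leave same-day admissions mixed with community tests.

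Fourth, 4.8.2 might be read as simply false. It is not: taking everyone tested avoids further selection among the tested, and the next sentence concedes changing criteria. What it omits is selection into testing.

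Finally, an analysis plan not shown might add a setting analysis. The protocol itself, however, fixes the population, the covariates and the named sensitivity analyses, and none of them covers setting.

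**Conclusion.** The point holds as a gap in the planned analysis of the third aim. The protocol pools everyone tested, recognises that some were already inpatients, and provides nothing that separates the two groups. A departure of the adjusted odds ratio from 1 without any drug effect is possible, chiefly against non-use. It requires that both ACE-I/ARB use (after adjustment) and positivity differ by setting.

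Size and direction cannot be determined from the document. The crude range of 0.76 to 1.10 rests on assumed inputs and is best treated as upper-end; with half the exposure gap it is 0.88 to 1.05. It would go too far to say that the pooled estimate will be biased, or that it will look protective: the illustrations fall on both sides of 1. The primary and secondary aims do not depend on this odds ratio. This is a worthwhile and inexpensive improvement, not a reason to discard the design.

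**What to change.** In section 4.9, pre-specify the adjusted odds ratios against non-use and against CCB use, stratified by admission status at the test (admitted before the test date, by the rule in 4.7, versus not). Report them beside the pooled odds ratio, which remains the main estimate. State that any conclusion on COVID-19 risk depends on agreement between the strata.

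In section 4.8.2, keep the sentence but qualify it: including all tested people avoids further selection among the tested, not selection into testing, and the expectation of equal testing has not been argued against non-users.

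Costs: section 4.7 needs the admission flag only for test-positive patients, so it must also be derived for the test-negatives (88,709 on the 20 April figures). The stratum estimates will be less precise than the pooled one. Because admission before the test may follow from COVID-19, the restricted odds ratio needs that caveat wherever it is reported.

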4.6. Exposure

The study is designed to address acute effects of current use of ACE-I/ARB, and we do not expect any cumulated effect of long-term ACE-I/ARB use. The half-life of ACE-I/ARB ranges from 1 to 24 hours.

The exposure will be defined by filled prescriptions for ACE-I/ARB and other antihypertensive drugs within 90 days before test for SARS-CoV-2. Data on prescriptions are obtained from the Danish Prescription Registry, which include complete and valid information on all filled prescriptions at community pharmacies in Denmark since 1995.²⁶ Data include, among others, date of dispensing, Anatomical Therapeutic Chemical (ATC) code, and drug quantity.

The main exposures will be:

- Current use (prescription filled within prior 90 days before test) of ACE-I/ARBs, compared with
 - Current use (prescription within 90 days) of calcium channel blockers (CCB), a cardiovascular drug used for similar medical indications as ACE-I and ARB, to assess if any observed association with outcomes is specific to ACE-I/ARB exposure.

• No use of ACE-I or ARB (prescription >365 days or never)

Secondary exposures will be:

- Former versus no use of ACE-I or ARB (former use defined as prescription 91-365 days before test)
- Current ACE-I/ARB use compared with:
 - Current use of thiazides (prescription within 90 days)
 - Current use of beta-blockers (prescription within 90 days)

As an additional analysis, ACE-I and ARB will be analyzed separately if the number of exposed are sufficient.

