4.8.3. Information bias

There may be some misclassification of the exposure, which will be addressed in a sensitivity analysis as described. Any misclassification is not expected to be associated with the outcomes of interest (non-differential misclassification), and any information bias are therefore expected to be towards the null.

As outcomes are accurately recorded, any misclassification is expected to be minor and not associated with the exposure.

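### The only planned check on exposure misclassification widens the fill window to 120 days, which does not address recent fillers who have stopped, the main remaining source of dilution in current use versus non-use

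*Protocol*

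**What the plan says.** Section 4.6 sets the target of inference: "The study is designed to address acute effects of current use of ACE-I/ARB". It adds: "The half-life of ACE-I/ARB ranges from 1 to 24 hours". Exposure is read from dispensing dates in three bands:

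- current use: "Current use (prescription filled within prior 90 days before test) of ACE-I/ARBs, compared with" CCB use or non-use as the main comparators;
- former use, a secondary exposure: "former use defined as prescription 91-365 days before test";
- non-use: "No use of ACE-I or ARB (prescription >365 days or never").

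On the prescription source, the same section says: "Data include, among others, date of dispensing, Anatomical Therapeutic Chemical (ATC) code, and drug quantity". None of the exposure definitions uses the quantity.

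Section 4.8.3 states: "There may be some misclassification of the exposure, which will be addressed in a sensitivity analysis as described". It expects any resulting bias to run towards the null. The only sensitivity analysis in the protocol that concerns exposure is in section 4.9: "repeating the analyses in patients who filled a prescription within 120 days before a positive test". The other two concern calendar time (4.9) and a 14-day follow-up for hospitalization (4.5).

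**The concern.** A fill-based definition of current use can go wrong in two ways. It can miss a continuing user who refills late, and it can count as current someone who has stopped. Widening the window addresses the first error. In the contrast with non-use, the first error is already largely dealt with by design, because the 91-365-day band keeps late refillers out of the comparator. The second error remains. For an acute effect of drugs with a half-life of hours, a person who stopped some time before the test is unexposed at the test but is counted as exposed.

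This is a safety question in which a result near 1 reassures. If the 90- and 120-day estimates agree, a reader of section 4.8.3 could take exposure misclassification as checked, when the error that pulls this contrast towards 1 has not been examined.

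**Working it through.** **Where a person falls (current use versus non-use, section 4.6)**

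| Last ACE-I/ARB fill before test | Main analysis | 120-day analysis |
|---|---|---|
| 0-90 days, still taking | current, correct | current, correct |
| 0-90 days, stopped | current, wrong | current, still wrong |
| 91-120 days, still taking | in neither group | current, correct |
| 91-120 days, stopped | in neither group | current, wrong |
| more than 365 days, or never | non-use | non-use |

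The second row is the main remaining source of dilution in the main contrast, and the wider window leaves it as it is.

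**Size of the dilution.** The protocol gives no figure for this. I take the RR of 1.2 from section 4.10 and assume that a share f of those counted as current has stopped and carries the unexposed risk p0. The risk in the group is then f·p0 + (1−f)·RR·p0, so

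observed RR = 1 + (1−f)(RR−1).

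- f = 10%: 1 + 0.9 × 0.2 = 1.18
- f = 20%: 1 + 0.8 × 0.2 = 1.16
- f = 30%: 1 + 0.7 × 0.2 = 1.14

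For a true RR of 1.5 the same shares give 1.45, 1.40 and 1.35.

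**What the 120-day run shows.** Let g be the number of 91-120-day fillers relative to 0-90-day fillers, and h the share stopped among them (both assumed). The stopped share becomes (f + g·h)/(1 + g), so the RR moves from the 90- to the 120-day window by

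−(RR−1) · g(h−f)/(1+g).

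The movement depends on h − f, not on f alone. With RR = 1.2 and g = 10%:

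| f | h | RR at 90 days | RR at 120 days |
|---|---|---|---|
| 0% | 50% | 1.200 | 1.191 |
| 20% | 50% | 1.160 | 1.155 |
| 30% | 50% | 1.140 | 1.136 |
| 30% | 30% | 1.140 | 1.140 |
| 20% | 10% | 1.160 | 1.162 |

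At h = 50% the movement is smallest where the dilution is greatest (f = 30%). At h = f nothing moves, whatever f is. In the last row the stopped share falls from 20% to (0.20 + 0.01)/1.10 = 19.1%. Agreement between the two windows is therefore compatible with any of these values of f.

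**Precision available to a stricter analysis.** Inputs from section 4.10 are 96,224 tested, 7,515 positive, 17% using ACE-I/ARB and 4% mortality in the unexposed. For simplicity everyone else is counted as non-use, and no loss from weighting is allowed for.

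- Death: 1,278 exposed and 6,237 unexposed, risks 4.8% and 4.0%. SE(log RR) = √[0.96/(0.04 × 6,237) + 0.952/(0.048 × 1,278)] ≈ 0.14. The 95% CI around 1.20 is about 0.91 to 1.58.
- Positive test, assuming 17% exposed among positives and among the 88,709 negatives: SE(log OR) = √(1/1,278 + 1/6,237 + 1/15,081 + 1/73,628) ≈ 0.03.

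A shift from 1.20 to 1.14 is ln(1.20/1.14) = 0.051 on the log scale: roughly 0.4 SE for death and 1.6 SE for the test-negative analysis.

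These inputs do not reproduce the 92% power stated in section 4.10 (about 27% two-sided). That is a separate matter, and nothing here depends on it.

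**The case against.** The strongest reply is that section 4.8.3 promises a sensitivity analysis and section 4.9 supplies one, that 4.8.3 openly expects bias towards the null, and that further exposure definitions could be left to a statistical analysis plan. This does not settle the point. The protocol itself names the check and gives it the job of addressing misclassification, and the mismatch between check and job lies within the protocol.

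Other objections stand, and they limit what may be claimed:

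- A reader might infer that the 120-day window can only keep or raise the share of stoppers. Their number cannot fall, but their share falls when h is below f. That older fillers include more stoppers is plausible; the protocol does not establish it.
- A reader might infer that the 120-day run could never reveal dilution. Marked attenuation at 120 days would be an indirect hint of stopping, although it would neither identify nor remove the stoppers among 0-90-day fillers.
- A reader might infer that the 120-day run is of no use. In the CCB contrast no gap is stated that removes recent ACE-I/ARB users, so a CCB user with an ACE-I/ARB fill 91-120 days ago could sit in the comparator. The wider window helps there.
- For death, dilution of this size lies well inside sampling error, and a stricter definition makes that worse. The objection has much less force for the test-negative analysis.
- A supply-based definition has its own errors. Section 4.6 names quantity but not daily dose or days' supply, and someone who stops before a pack runs out still counts as current.

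**Conclusion.** The point holds as a cheap improvement and is limited to current use versus non-use. The one exposure sensitivity analysis does not address the main remaining source of dilution in that contrast, and agreement between the 90- and 120-day results would not show that the dilution is small.

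That conclusion follows from the definitions in section 4.6. Its size does not: an observed RR of 1.18, 1.16 or 1.14 for a true 1.2 rests on assumed stopped shares of 10%, 20% or 30%, and on stoppers having the unexposed risk. The documents do not support a claim that the main results are materially biased.

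**What to change.** Keep the 120-day analysis. Add one prespecified sensitivity analysis in the opposite direction, applied identically to ACE-I/ARB, CCB, thiazides and beta-blockers, with one of these definitions of current use:

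- a fixed fill window shorter than 90 days; or
- coverage of the test date by the recorded dispensed quantity, with the assumed one unit per day and a fixed grace period stated, and stock from earlier fills carried forward.

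In section 4.8.3, state which error each analysis covers: the 120-day window for long refill intervals and for recent ACE-I/ARB users in the active-comparator groups, and the stricter definition for people counted as current who have stopped.

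The cost is one more run on variables already held. There will be fewer exposed patients and wider confidence intervals in that analysis, especially for death. It reduces misclassification without eliminating it, and should be reported in those terms.
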